__15. Known active central nervous system (CNS) involvement by lymphoma, including leptomeningeal involvement.

__16. Clinically significant cardiovascular disease such as symptomatic arrhythmias, congestive heart failure, or myocardial infarction within 6 months of screening, or any Class III or IV cardiac disease as defined by the New York Heart Association Functional Classification. Note: Subjects with controlled, asymptomatic atrial fibrillation can enroll on study. See [Appendix B](#).

__17. Unstable angina (angina symptoms at rest), new-onset angina (begun within the last 6 months).

__18. History of or current progressive multifocal leukoencephalopathy (PML).

__19. Inability to swallow and retain an oral medication.

__20. Clinically significant uncontrolled illness, including active infection requiring antibiotics.

__21. Live virus vaccines within 4 weeks of start of protocol therapy or planned administration of live virus vaccines during ublituximab therapy.

__22. Evidence of chronic active Hepatitis B (HBV, not including patients with prior hepatitis B vaccination; or positive serum Hepatitis B antibody) or chronic active Hepatitis C infection (HCV), or active cytomegalovirus (CMV). If HBc antibody is positive, the subject must be evaluated for the presence of HBV DNA by PCR. If HCV antibody is positive, the subject must be evaluated for the presence of HCV RNA by PCR. (See [Appendix J](#): Hepatitis B serologic test results). If the subject is CMV IgG or CMV IgM positive, the subject must be evaluated for the presence of CMV DNA by PCR. Subjects with positive HBc antibody and negative HBV DNA by PCR are eligible. Subjects with positive HCV antibody and negative HCV RNA by PCR are eligible. Subjects who are CMV IgG or CMV IgM positive but who are CMV DNA negative by PCR are eligible. Patients with a prior known history of hepatitis B and those with a positive anti-HBc with negative HBsAg at screening must be able to receive antiviral agents effective against hepatitis B.

__23. Known history of human immunodeficiency virus (HIV) infection.

Patient MRN (COH Only)	Patient Initials (F, M, L):
------------------------	-----------------------------

Institution:

24. *Females only:* Pregnant or breastfeeding

25. Any other condition that would, in the Investigator's judgment, contraindicate the patient's participation in the clinical study due to safety concerns with clinical study procedures.

Noncompliance

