4.2.3 Registration Process

Allow up to 24 hours for the DCC to review eligibility. To register a participant the subsequent procedure is to be followed:

1. The study team should contact the DCC via email to provide notification regarding the pending registration and communicate desired timeline of the registration, especially if it must be completed promptly to meet the registration window.
2. The study team will email a **Complete Registration Packet** to the DCC, which consists of a copy of the following documents:
 - Registration Cover Sheet ([Appendix D](#))
 - Completed eligibility checklist (printed from [Section 3.0](#) of the protocol) with required signature(s)
 - Source documents that support all eligibility criteria listed in the eligibility checklist
 - Signed Informed Consent
 - Signed HIPAA authorization form (if separate from informed consent)
 - Signed subject's bill of Rights (California only)
3. In some cases, the DCC may request additional documentation prior to registration. Please refer to the Work Instruction – Reviewing Packets and Registering Subjects for more information. A copy of this work instruction can be provided by the DCC, upon request.
4. When all source documents are received, the DCC will review to verify eligibility, working with the study team to resolve any missing required source elements. Any missing documents may delay review and

registration. A participant failing to meet all protocol eligibility requirements will not be registered and the study team will be immediately notified.

5. Once eligibility is confirmed, the DCC will send a Confirmation of Registration Form and signed Eligibility Checklist, including the Subject Study Number and cohort assignment to:
 - The study team: Site Lead Investigator, treating physician/ sub-investigator, protocol nurse, CRC and pharmacy (as needed).
 - The COH Study PI and COH study team designees (including but not limited to study monitor(s) and statistician(s)).
6. Upon receipt of the Confirmation of Registration Form, COH study team will register the patient in OnCore. The DCC will register non-COH patients in OnCore.

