Hemorrhage	
Serious hemorrhagic events, including fatal events, have occurred in clinical trials with acalabrutinib.
 
The mechanism for hemorrhage is not well understood. Patients receiving antithrombotic agents may be at increased risk of hemorrhage. Use caution with antithrombotic agents and consider additional monitoring for signs of bleeding when concomitant use is medically necessary.
 
Consider the benefit-risk of withholding acalabrutinib for at least 3 days pre- and post-surgery.
 
Subjects with hemorrhage should be managed per institutional guidelines with supportive care and diagnostic evaluations as clinically indicated.

Infections	
Serious infections (bacterial, viral, and fungal), including fatal events, have occurred in clinical studies with acalabrutinib. The most frequent reported Grade ≥ 3 infection was pneumonia (preferred term). Across the acalabrutinib clinical development program (including subjects treated with acalabrutinib in combination with other drugs), cases of hepatitis B virus (HBV) reactivation, aspergillosis, and progressive multifocal leukoencephalopathy (PML) have occurred.
 
Consider prophylaxis in subjects who are at increased risk for opportunistic infections. Subjects should be monitored for signs and symptoms of infection and treated as medically appropriate.
 
Subjects with infection events should be managed according to institutional guidelines with maximal supportive care and diagnostic evaluations as clinically indicated.

Cytopenias	Treatment-emergent Grade 3 or 4 cytopenias, including neutropenia, anaemia, and thrombocytopenia have occurred in clinical studies with acalabrutinib. Monitor blood counts as specified in the schedule of assessments and as medically appropriate.

	Subjects with cytopenias should be managed according to institutional guidelines with maximal supportive care and diagnostic evaluations as clinically indicated. Subjects should be closely monitored as appropriate.

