APPENDIX J: HEPATITIS B SEROLOGIC TEST RESULTS

Interpretation of Hepatitis B Serologic Test Results

Hepatitis B serologic testing involves measurement of several hepatitis B virus (HBV)-specific antigens and antibodies. Different serologic "markers" or combinations of markers are used to identify different phases of HBV infection and to determine whether a patient has acute or chronic HBV infection, is immune to HBV as a result of prior infection or vaccination, or is susceptible to infection.

HBsAg anti-HBc anti-HBs	negative negative negative	Susceptible
HBsAg anti-HBc anti-HBs	negative positive positive	Immune due to natural infection
HBsAg anti-HBc anti-HBs	negative negative positive	Immune due to hepatitis B vaccination
HBsAg anti-HBc IgM anti-HBc anti-HBs	positive positive positive negative	Acutely infected
HBsAg anti-HBc IgM anti-HBc anti-HBs	positive positive negative negative	Chronically infected
HBsAg anti-HBc anti-HBs	negative positive negative	Interpretation unclear; four possibilities: 1. Resolved infection (most common) 2. False-positive anti-HBc, thus susceptible 3. "Low level" chronic infection 4. Resolving acute infection

Adapted from: A Comprehensive Immunization Strategy to Eliminate Transmission of Hepatitis B Virus Infection in the United States: Recommendations of the Advisory Committee on Immunization Practices. Part I: Immunization of Infants, Children, and Adolescents. MMWR 2005;54(No. RR-16).

■ **Hepatitis B surface antigen (HBsAg):**

A protein on the surface of hepatitis B virus; it can be detected in high levels in serum during acute or chronic hepatitis B virus infection. The presence of HBsAg indicates that the person is infectious. The body normally produces antibodies to HBsAg as part of the normal immune response to infection. HBsAg is the antigen used to make hepatitis B vaccine.

■ **Hepatitis B surface antibody (anti-HBs):**

The presence of anti-HBs is generally interpreted as indicating recovery and immunity from hepatitis B virus infection. Anti-HBs also develops in a person who has been successfully vaccinated against hepatitis B.

■ **Total hepatitis B core antibody (anti-HBc):**

Appears at the onset of symptoms in acute hepatitis B and persists for life. The presence of anti-HBc indicates previous or ongoing infection with hepatitis B virus in an undefined time frame.

■ **IgM antibody to hepatitis B core antigen (IgM anti-HBc):**

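### Exclusion 22 states no explicit eligibility consequence for a positive screening HBsAg, so a newly found HBsAg-positive, HBV DNA-negative patient can be enrolled outside the mandatory hepatitis B prophylaxis rule

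*Combined protocol and SAP*

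**What the plan says.** **Eligibility.** Exclusion 22 opens with "Evidence of chronic active Hepatitis B (HBV, not including patients with prior hepatitis B vaccination; or positive serum Hepatitis B antibody" and closes the parenthesis there. It requires HBV DNA testing when anti-HBc is positive, refers to Appendix J, and then states: "Subjects with positive HBc antibody and negative HBV DNA by PCR are eligible". HBsAg appears in the item only in its negative form, in the last sentence: "Patients with a prior known history of hepatitis B and those with a positive anti-HBc with negative HBsAg at screening must be able" to receive antivirals active against hepatitis B.

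**Testing.** Section 10.0, footnote w, puts HBsAg and HBc antibody in the screening panel. The trigger for HBV PCR is a positive HBc antibody, and the PCR is described as the test for active virus. A positive HBsAg is not a trigger.

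**Interpretation.** Appendix J labels the two HBsAg-positive profiles "Acutely infected" and "Chronically infected". It is an interpretation table and contains no eligibility rule.

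**Safeguards.** Section 5.4.1 makes HBV-effective prophylaxis mandatory for two groups: patients with a prior *known* history of hepatitis B, and patients who are anti-HBc-positive with a negative HBsAg. Section 5.5.1 (monitoring), Section 5.10 and the triple-asterisk footnote to Table 7.1.1 (holding ublituximab when liver enzymes rise) use the same serology group, but say prior history without the word known.

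**Hazard.** Section 6.1 lists hepatitis B reactivation as a serious ublituximab risk with a frequency below 0.1%. Table 6.2.3 says of the acalabrutinib programme, combinations included, that "cases of hepatitis B virus (HBV) reactivation, aspergillosis, and progressive multifocal leukoencephalopathy (PML) have occurred".

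**The concern.** The test that Appendix J uses to identify current infection is done at screening, but the criterion does not say what follows from a positive result. The most specific sentence in the item grants eligibility on two results, anti-HBc and HBV DNA, and is silent on the third. The prophylaxis rule is conditioned on that third result being negative.

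Together these give an inverted outcome. An anti-HBc-positive patient with a negative HBsAg must receive prophylaxis. A patient with the same anti-HBc and DNA results but a positive HBsAg need not. Two of the three study drugs carry a stated reactivation risk and are given for up to 25 cycles, so the matter is one of individual patient safety. It does not bear on the trial's inference.

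**Working it through.** The plan gives no figure on this point, so the check follows one patient through the rules as written: HBsAg-positive, anti-HBc-positive, HBV DNA-negative, no hepatitis B history known before screening.

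1. *Lead phrase of exclusion 22.* The patient must show chronic active disease. Anti-HBc triggers PCR and the PCR is negative, so in footnote w's terms active virus was not found. Appendix J would call the patient infected, but does not define chronic active. The parenthesis also sets aside antibody-positive patients, which on one reading points toward eligibility.
2. *Eligibility sentence of exclusion 22.* Positive anti-HBc: met. Negative HBV DNA: met. There is no third condition, so the patient is eligible as written.
3. *Antiviral clause of exclusion 22.* Prior known history: not met. Anti-HBc-positive with negative HBsAg: not met. The clause does not apply.
4. *Mandatory prophylaxis, Section 5.4.1.* Same two groups, neither met. Prophylaxis is not required.
5. *Monitoring (5.5.1) and hold rules (5.10, Table 7.1.1 footnote).* The serology group is not met. Prior history is open to argument, because an infection found at screening precedes Day 1. Coverage is uncertain.

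The two DNA-negative, anti-HBc-positive results compare as follows:

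| | HBsAg negative | HBsAg positive, newly found |
|---|---|---|
| Eligibility sentence | met | met |
| Antiviral clause (exclusion 22) | applies | does not apply |
| Mandatory HBV prophylaxis (5.4.1) | required | not required |
| Monitoring and hold rules | apply | uncertain |

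**Counting profiles.** Appendix J lists 6 profiles, of which 4 are anti-HBc-positive: natural infection, acute, chronic and unclear. Of those 4, 2 are HBsAg-negative and covered by the safeguards' serology wording, and 4 − 2 = 2 are HBsAg-positive and not covered. The acute and chronic rows differ only in IgM anti-HBc, which footnote w does not list. On the stated panel they are therefore a single screening result. These are rows of a table, not patients, and say nothing about frequency.

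**Does the general antiviral prophylaxis fill the gap?** Section 5.10 requires antiviral prophylaxis for everyone on umbralisib and recommends Valtrex or acyclovir. Section 5.4.1 states the HBV-effective requirement as a separate item for a restricted group. The protocol therefore does not treat the first as satisfying the second.

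**The case against.** **The item should be read as a whole.** The eligibility sentence is the first of three parallel sentences, for HBV, HCV and CMV. Each closes out an antibody-triggered PCR work-up, and nothing says that any of them overrides the lead exclusion. The lead phrase and the Appendix J pointer suggest that a positive HBsAg was meant to exclude. The safeguards' repeated wording is coherent on exactly that assumption. This stands as evidence of intent, and it rules out the inference that the plan gives a positive HBsAg no bearing on eligibility, or deliberately admits such patients. What is missing is an *explicit* consequence.

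**Other protections exist.**
- Sites submit "Source documents that support all eligibility criteria listed in the eligibility checklist", and "the DCC will review to verify eligibility". The review is made against the checklist that contains the open sentence, and the sign-off table in Section 3 allows a study nurse or coordinator as confirmer.
- Exclusion 25 leaves room for investigator judgment, but is discretionary.
- Section 5.10 calls for clinically indicated prophylaxis under institutional policy, and Table 6.2.3 asks that prophylaxis be considered for those at increased risk of opportunistic infection. Neither mandates HBV prophylaxis.
- The liver rules in Table 7.1.1 require a check for viral infection and labs every 1–2 weeks at Grade 1, a hold of all three drugs at Grade 2, and a viral hepatitis check before steroids. They act only after enzymes rise, and at Grade 1 ublituximab continues unless the hepatitis B footnote applies.

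These make harm less likely. None replaces the missing condition.

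**The size is small.** Exposure needs four things together (HBsAg-positive, anti-HBc-positive, DNA-negative, no known history), and nobody acting on the HBsAg result. That is correct. A reader might infer from the profile count that half of anti-HBc-positive patients go unprotected. The documents do not support this: the count is of table rows, the two uncovered rows are one result on the stated panel, and no prevalence is given.

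**Conclusion.** The point holds as a wording gap with a safety consequence. Two safeguards are clearly missed for the newly found HBsAg-positive, DNA-negative patient: the antiviral clause of exclusion 22 and mandatory prophylaxis in Section 5.4.1. A reader might go further and infer that every hepatitis B safeguard is missed. The text does not support that, because the monitoring and hold rules turn on prior history and can be read to include this patient. A patient whose hepatitis B was known before screening is covered throughout.

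Few if any of the maximum 27 patients would be affected. The documents give no HBsAg prevalence, so no expected number is offered. Sample size, error rates and efficacy estimates do not change. The conclusion assumes that sites apply the eligibility sentence as written; many investigators would probably exclude or treat such a patient anyway. Minor severity: a cheap improvement for patient safety.

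**What to change.** In exclusion 22, make the eligibility sentence require three results: positive HBc antibody, negative HBsAg and negative HBV DNA by PCR. Add a statement that HBsAg-positive subjects are excluded. This aligns eligibility with the safeguards as they are now worded, and also settles the case of a positive HBsAg with negative anti-HBc, for which no PCR trigger is stated.

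If the sponsor does mean to enrol HBsAg-positive, DNA-negative patients, the alternative is to extend to any HBsAg-positive subject the antiviral clause (exclusion 22), prophylaxis (5.4.1), monitoring (5.5.1), the hold rules (5.10 and the Table 7.1.1 footnote) and the PCR trigger (exclusion 22 and footnote w).

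The first option costs a few words in one criterion and no new procedure, since HBsAg is already in the screening panel. Its downside is that at most a very small number of screened patients become ineligible.

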4.0 PARTICIPANT ENROLLMENT

NOTE: Sites must meet activation requirements prior to enrolling participants.

4.1 Pre-Enrollment Informed Consent and Screening Procedures

Diagnostic or laboratory studies performed exclusively to determine eligibility will be done only after obtaining written informed consent. Studies or procedures that are performed for clinical indications (not exclusively to determine study eligibility) may be used for baseline values and/or to determine pre-eligibility, even if the studies were done before informed consent was obtained.

The informed consent process is to be fully documented (see [Section 17.4](#)), and the prospective participant must receive a copy of the signed informed consent document. Screening procedures are listed in [Section 10.0](#) (Study Calendar).

4.2 Participant Enrollment

4.2.1 COH DCC Availability and Contact Information

Eligible participants will be registered on the study centrally by the Data Coordinating Center (DCC) at City of Hope. DCC staff are available **between the hours of 8.00 am and 5.00 pm PST, Monday through Friday (except holidays).**

- E-mail: [contact]

4.2.2 Slot verification and reservation

A designated study team member should email the DCC to verify current slot availability, and to reserve a slot for a specific prospective subject (provide DCC with subject initials), including a tentative treatment date. Slots can only be held for a limited time, at the discretion of the study PI.

The DCC should be notified of cancellations of prospective participants holding slots as soon as possible.

4.2.3 Registration Process

Allow up to 24 hours for the DCC to review eligibility. To register a participant the subsequent procedure is to be followed:

1. The study team should contact the DCC via email to provide notification regarding the pending registration and communicate desired timeline of the registration, especially if it must be completed promptly to meet the registration window.
2. The study team will email a **Complete Registration Packet** to the DCC, which consists of a copy of the following documents:
 - Registration Cover Sheet ([Appendix D](#))
 - Completed eligibility checklist (printed from [Section 3.0](#) of the protocol) with required signature(s)
 - Source documents that support all eligibility criteria listed in the eligibility checklist
 - Signed Informed Consent
 - Signed HIPAA authorization form (if separate from informed consent)
 - Signed subject's bill of Rights (California only)
3. In some cases, the DCC may request additional documentation prior to registration. Please refer to the Work Instruction – Reviewing Packets and Registering Subjects for more information. A copy of this work instruction can be provided by the DCC, upon request.
4. When all source documents are received, the DCC will review to verify eligibility, working with the study team to resolve any missing required source elements. Any missing documents may delay review and

registration. A participant failing to meet all protocol eligibility requirements will not be registered and the study team will be immediately notified.

5. Once eligibility is confirmed, the DCC will send a Confirmation of Registration Form and signed Eligibility Checklist, including the Subject Study Number and cohort assignment to:
 - The study team: Site Lead Investigator, treating physician/ sub-investigator, protocol nurse, CRC and pharmacy (as needed).
 - The COH Study PI and COH study team designees (including but not limited to study monitor(s) and statistician(s)).
6. Upon receipt of the Confirmation of Registration Form, COH study team will register the patient in OnCore. The DCC will register non-COH patients in OnCore.

4.3 Screen Failures and Registered Participants Who Do Not begin Study Treatment

Notify the DCC immediately if the participant screen fails after registration or if the participant does not start treatment.

For non-COH sites, the reason for screen failure will be documented in the registration coversheet ([Appendix D](#)) and submitted to the DCC.

Issues that would cause treatment delays should be discussed with the Study Principal Investigator.

5.0 TREATMENT PROGRAM

5.1 Treatment Program Overview

This is a multicenter, open-label, single cohort, phase 2 study of BTK inhibitor acalabrutinib and PI3K δ umbralisib in combination with ublituximab (AU2) for patients with previously untreated mantle cell lymphoma (MCL).

The trial consists of an Induction phase (6 cycles), followed by a Maintenance phase (19 cycles) for a total of 25 cycles of protocol therapy. Participants with stable disease (SD) or better response at the end of Induction will be eligible to proceed to Maintenance. At the end of Maintenance, participants may be allowed to continue therapy with acalabrutinib per treating physician's decision. For both Induction and Maintenance, each cycle will be 28 days.

Please refer to the [Study Schema](#) for additional details.

Participants who end protocol therapy will undergo follow-up ([Section 5.7](#)). Windows for all assessments and treatments are detailed in [Section 10](#).

5.2 Cycle Definition

In the absence of a delay due to toxicity, each treatment cycle lasts 28 days with a \pm 3 day window during Induction and 28 days with a \pm 7 day window during Maintenance.

During the Induction phase (Cycles 1-6), Day 1 of each cycle is defined as the first day of administration of ublituximab.

During the Maintenance phase (Cycles 7-25), ublituximab is administered every 2 cycles (every 8 weeks) starting on Day 1 of Cycle 8, and each cycle is defined as 28 days.

